10. ANALYSIS CORRESPONDING TO THE STUDY OBJECTIVES

Overall Survival (OS) is defined as the time from a patient's date of Day 0 until date of death. Patients still alive will be censored at withdrawal from the study or at last known date alive if later (where patients have consented to follow-up for overall survival outcome, after they have withdrawn from the study). If consent has been provided by the patient, the patient's final outcome will be included if death and if alive, the patient will have censored outcome at the date last known to be alive.

Post-study survival status after withdrawal from the study, for any withdrawn patients, will be recorded on a separate Post-study Long Term Survival Status CRF, and these data will be included in the analysis and data listings, as described above.

The patient's death is recorded as the date of study completion on CRF page 18 and if after withdrawal from the study, the date of death recorded on the Post-study CRF.

A patient without a death date will be censored in the analysis at the last date known to be alive providing their consent was obtained. Patients withdrawing from the study without consent for further follow up will be censored for survival at the date of their withdrawal from the study (recorded on CRF page 18).

Overall Survival will be summarised by Kaplan-Meier curves. Median, 25% and 75% survival estimates as well as associated 95% CIs will be reported in Table 8 and Figure 2.

SAS procedure output for the OS analysis will be included as an appendix to the CSR.

The changes in metastatic disease compared with previous assessment (as measured via CT or MRI scan) recorded at the discretion of the investigator, will be presented over the treatment period in data listings only (Listing 11).

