### **6.3 PATIENT WITHDRAWAL CRITERIA**

#### **6.3.1 Removal of Patients from Therapy or Assessment**

The patient will be advised in the ICF that they have the right to withdraw from the study at any time without prejudice, and may be withdrawn at the Investigator's or the Sponsor's discretion at any time.

In the event that the patient drops out of the study or is withdrawn from the study, the withdrawal page in the patient's CRF should be completed. On the withdrawal page the

---

CONFIDENTIAL

Immudon Therapeutics Ltd.  
[name]

Investigator (or designee) should record the date of the withdrawal, the person who initiated withdrawal and the reason for withdrawal.

The following are reasons for patient dropout/withdrawal:

Withdrawn by the Investigator due to:

- Adverse event.
- Protocol violation or non-compliance with the Protocol.
- Intolerable injection site reaction.
- Pregnancy.
- Toxicity.
- Other reasons.

Withdrawal requested by the patient due to:

- An AE for which the Investigator did not consider removal from the study necessary.
- Withdrawal of consent.
- Other.

Other:

- Lost to follow-up.
- Administrative problems.

Reasonable effort should be made to contact any patient lost to follow-up during the course of the study in order to complete assessments and retrieve any outstanding data.

For patients who leave the study or when the study ends, normal standards of care, according to local practice, will continue as necessary. In the case of withdrawal, separate consent will be sought to allow the continued collection on patient status.

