#### **Overall Survival (OS)**

OS is defined as the time from enrolment to death due to any cause. OS will be expressed from time of initial diagnosis, time of enrolment in the Phase 1 study as well as from time of enrolment in this long term follow up study.

Patients without a death date will be censored at the date the patient was last known to be alive.

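### SAP section 10 can censor survival at a recorded withdrawal date that is later than the last contact; the supplied protocol censors at the date last known alive, and the SAP does not declare the difference

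*SAP*

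**What the plan says.** Section 8.1 of the supplied protocol, under Overall Survival, has a single rule with no consent condition: "Patients without a death date will be censored at the date the patient was last known to be alive".

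SAP section 10 has three statements that bear on the same date:

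- The general statement: "Patients still alive will be censored at withdrawal from the study or at last known date alive if later". A parenthesis ties the second option to patients who consented to survival follow-up after withdrawal.
- For consenting patients: "A patient without a death date will be censored in the analysis at the last date known to be alive providing their consent was obtained".
- For the rest: "Patients withdrawing from the study without consent for further follow up will be censored for survival at the date of their withdrawal from the study". This date is taken from CRF page 18.

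The censored date enters the survival formula in SAP section 8.3 and then Table 8 and Figure 2.

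Protocol 6.3.1 sets out what counts as a withdrawal. Its list of reasons includes "Lost to follow-up" and administrative problems. On the date itself it says only that the "Investigator (or designee) should record the date of the withdrawal, the person who initiated withdrawal and the reason for withdrawal". On later status it says: "In the case of withdrawal, separate consent will be sought to allow the continued collection on patient status".

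SAP section 11 declares one change to overall survival, the move of the time origin from enrolment to Day 0. SAP section 4 explains why the other two time origins were dropped. Neither section mentions censoring.

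**The concern.** A withdrawal date is a safe censoring date when the patient was seen or spoken to that day. It is not safe when it marks an administrative act. A patient lost to follow-up has no contact on the day the withdrawal is entered, and is unlikely to have given the separate consent, because that is sought at withdrawal. Such a patient therefore tends to fall under the withdrawal-date rule.

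Study closure raises the same question. The Listing 1 shell allows only two off-study statuses, died or withdrawn, and notes that the trial was terminated in December 2018. Anyone alive and on study at that point is presumably recorded as withdrawn, on a date that may or may not be a contact.

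If the recorded date is later than the last contact, the patient is treated as known alive when nobody knows. The denominator at any death in that gap is then too large. Overall survival is the only efficacy endpoint the SAP summarises, since change in metastatic disease is listed only, and in a small cohort one patient can move a step visibly.

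**Working it through.** The plan gives no survival figure, sample size or event count, so there is nothing to reproduce. The check compares the rules and then sizes the effect under stated assumptions.

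**Rules side by side.** Let W be the recorded withdrawal date and L the last date known alive.

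| Situation | Supplied protocol 8.1 | SAP section 10 |
|---|---|---|
| Withdraws in person, no later contact (L = W) | W | W |
| L before W, no consent | L | W (later than protocol) |
| L before W, consent held | L | W by the general sentence, L by the consent sentence |
| Reached by telephone after W for adverse event follow-up, no status consent (L after W) | L | W (earlier than protocol) |

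The third row is a conflict within the SAP. It should be uncommon: consent is sought at withdrawal and is itself evidence of life, so L before W needs a consent that predates the recorded withdrawal. The second row is the one that matters for the curve.

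**One Kaplan-Meier step.** Let r patients be truly under observation at a death and k patients be kept at risk after last contact. The step factor is (r − 1)/r when only observed patients count, and (r + k − 1)/(r + k) when the extra patients are kept.

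- r = 6, k = 1: 5/6 = 0.833 against 6/7 = 0.857, ratio 1.029.
- r = 4, k = 2: 3/4 = 0.750 against 5/6 = 0.833, ratio 1.111.

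Each requires a death inside the gap. The second also requires two such patients at once with only four others at risk.

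**A whole curve.** Assumptions: 10 patients (the documents give no number; 10 is suggested only by the 2×5 panel layout in Figures 1a and 1b), deaths at 1, 2, 3, 4 and 5 years, one patient last contacted at 1.9 years, and four followed to 7 years.

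- Censored at last contact: S(2) = 9/10 × 7/8 = 0.7875; S(5) = 0.7875 × 6/7 × 5/6 × 4/5 = 0.450.
- Censored 3 or 6 months later: S(2) = 9/10 × 8/9 = 0.800; S(5) = 0.800 × 6/7 × 5/6 × 4/5 = 0.457.
- Censored 1 month later (about 1.98 years): no death falls in the gap and nothing changes.

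The median is 5.0 years in every case.

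**Expected size.** Simulation with 10 patients, exponential survival with a 5-year median, 7 years of follow-up, last contact of lost patients uniform over 0 to 6 years, and 3,000 runs per cell. Mean increase in S(5) from censoring at withdrawal instead of last contact:

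| Patients lost | 1-month gap | 6-month gap | 12-month gap |
|---|---|---|---|
| 1 | 0.0005 | 0.0027 | 0.0055 |
| 2 | 0.0010 | 0.0058 | 0.0119 |
| 3 | 0.0018 | 0.0090 | 0.0178 |

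The largest rise in any single run was 0.188. No run showed a fall, but only withdrawal dates after last contact were modelled, so this says nothing about the fourth row of the first table. The gaps are assumptions. Protocol 5.2 allows attendance as rarely as every 6 months, with a telephone call if a calendar month passes without a visit. The call shortens the gap for patients who answer, but not for those who cannot be reached.

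**The case against.** The strongest reply is that the harm depends on a fact the documents do not contain. Protocol 6.3.1 asks for the date of withdrawal but does not define it for an unreachable patient, and CRF page 18 is not supplied. If sites entered the last contact date, the rules agree. Nor is any affected patient shown: the withdrawal reasons in the Table 1 shell include neither loss to follow-up nor administrative problems, only a residual category. That does not show that nobody was lost. This reply stands, and it limits the point to what the rule permits.

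A reader might infer that the survival curve is biased upwards. The documents do not support that. Bias needs a patient with a gap and a death inside it. The no-consent rule can also work the other way: adverse events are followed for 30 days after withdrawal, by telephone if needed, so a non-consenting patient may be known alive after the date at which the SAP censors. A reader might also infer that lost patients do worse. No source is given for that, and if it were true, censoring at last contact would not remove the informative censoring.

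Two further replies have partial force. First, protocol 10.6 lets deviations be documented in the final SAP, and section 10 states its rule openly; what is missing is any acknowledgement or reason. Second, the no-consent sentence respects the protocol's requirement of separate consent for later status. That explains not looking beyond withdrawal, but not counting a patient as alive up to a date without contact.

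**Conclusion.** The textual point holds. SAP section 10 departs from section 8.1 of the supplied protocol, its own sentences disagree for consenting patients when the dates differ, and the departure is neither declared nor justified. A reader might call this a breach of the governing protocol, but that cannot be established: SAP section 1 cites version 9.0, incorporating amendment 8.0, while the supplied protocol's amendment log ends at 7.0.

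Followed literally, the rule keeps a patient at risk without known status whenever withdrawal is recorded after the last contact. That is possible for loss to follow-up, administrative withdrawal and closure at study termination. If a death falls in the gap, the step is too high, for example 0.857 instead of 0.833 with six others at risk. The expected effect is small, a mean rise in S(5) of about 0.0005 to 0.018 under the assumptions above, and the median was unchanged in the worked example. SAP section 4 rules out formal inference, and protocol 3.4 says the study is not designed to show efficacy. The correction is worth making because it is cheap and removes an ambiguity a programmer would otherwise have to settle alone.

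**What to change.** In SAP section 10, replace the three censoring statements with one rule. Every patient without a death date is censored at the last date documented alive, taken as the latest of: a study visit, a dose, a recorded telephone contact (including permitted adverse event follow-up), or a consented post-study status assessment. The withdrawal date counts only when it was itself a contact with the patient. Use this date in the section 8.3 formula, Table 8 and Figure 2.

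If the sponsor prefers to keep the withdrawal date, section 11 should say so, give the reason, and state how that date was set for patients not in contact on the day.

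The cost is a short rewording and one derived date. Visit, dose and post-study status dates are already listed (Listings 10, 15 and 17). Some call dates may have to be checked in the patient notes, where protocol 5.2 has call details recorded. Follow-up becomes slightly shorter for some patients.

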### **2. Treatment**

Patients can receive ongoing treatment every 4 weeks or as close to this interval as permitted due to practical or logistic considerations until death or withdrawal, unless such therapy is contraindicated, the patient does not wish to continue or the study is terminated by the Sponsor. At no point should the elapsed period between IMM-101 doses be less than 14 days. The Study Flow Chart of Assessments is provided as Appendix 1.

Patients may choose to withdraw from the study at any time and for any reason. IMM-101 should be stopped or the dosing regimen reduced if felt to be necessary by the Investigator and/or patient (e.g., intolerable injection site reactions). In the event of an injection site reaction of Grade 3 and above, and/or if significant ulceration, tenderness or lymphadenopathy is observed, at the discretion of the Investigator, patients may be administered a half dose of the study drug (i.e., a single 0.05 mL intradermal injection of IMM-101) or the timing of the injection may be delayed. If the dosing interval is increased, the patient should still attend the study site for safety assessments preferably every 3 months but, if this is not possible, every 6 months at a minimum. In addition, if the patient does not attend the clinic for a study visit within a calendar month, the clinic will telephone the patient to enquire about injection site reactions, adverse events, concomitant medications and any other concerns. Details of the call will be recorded in the patient notes with appropriate information on adverse events and concomitant medications also being recorded in the CRF. The blood sample for exploratory analysis should continue to be taken every 6 months.

Any change in the dose of study drug administered or the frequency of dose administration should be recorded in the patient's case report form (CRF). In the case of withdrawal, separate consent will be sought to allow the continued collection on patient status.

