### **SUMMARY OF PROTOCOL AMENDMENTS**

#### **PROTOCOL AMENDMENT 1.0**

This Protocol amendment, dated 21st November 2011, addressed the following change to the study Protocol (Final Version 1.0, dated 15th September 2011):

1. To reduce the volume of blood taken at six monthly intervals for the analysis of exploratory immunological endpoints.

This Protocol Amendment was considered **non-substantial**.

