#### **PROTOCOL AMENDMENT 4.0**

This protocol amendment, dated 1st November 2013 addressed the following changes to the study Protocol (Final Version 4.0, dated 1st July 2012):

- Inclusion of collection of information on subject status following withdrawal from the study subject to provision of informed consent

This Protocol Amendment was considered **non-substantial**.

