1. INTRODUCTION

The study explores the long-term safety and tolerability of continued administration of IMM-101 in patients who were previously enrolled in the Phase I safety and tolerability study, IMM-101-001. IMM-101-001 was a first-in-human (FIH), open-label, dose-escalation, intra-patient, placebo-controlled study, in adult patients with confirmed diagnosis of stage III or IV melanoma to evaluate the safety and tolerability of three doses of IMM-101 (further details are available in the FIH study clinical study report [CSR]).

In this long-term follow-up (LTF) study, IMM-101-008, IMM-101 (10 mg/mL) is administered as a single 0.1 mL intradermal injection every 4 weeks or as close to this interval as permitted due to practical or logistical considerations until death or withdrawal, unless such therapy is contraindicated, the patient does not wish to continue, or the study is terminated by the Sponsor.

The duration of this study is determined by the time to death or withdrawal of the last patient remaining in this study, hence the total duration of the study is not pre-determined.

This Statistical Analysis Plan (SAP) describes the intended statistical evaluation of the study data at the time of final study reporting based on the final study database.

This SAP is based on the study protocol (version 9.0, dated 18 October 2017, incorporating amendment numbers 1.0 to 8.0) and the final study case report form (CRF), version 4, dated 02 December 2012, the amended adverse event (AE) CRF version 3, dated 15 October 2013, and Post-Study Long Term Survival Status CRF version 1.0, dated 28 September 2015.

This SAP incorporates the original objectives outlined in the study protocol, the approved SAP dated 08 October 2015 and further amendments combining relevant data from the FIH study IMM-101-001 with the final study data for the LTF study IMM-101-008, in IMM-101-008-enrolled patients, thus providing an evaluation of the long-term safety profile of IMM-101 from first dosing in the FIH study through to last dosing in the LTF study, including the period between studies when patients were treated with IMM-101 under the Immodulon Named Patient Programme (NPP), when relevant data has been recorded in the LTF study CRF.

The FIH study results are reported in the CSR (date 01 March 2011), based on the final FIH study CRF version date 25 January 2010 and the final study database.

2. STUDY OBJECTIVE(S) AND ENDPOINT(S)**2.1 Study Objective(s)**

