Post-Study Long Term Survival Status

Unique Patient ID	Date of Consent For Data Collection	Date of Assessment of Status (DD-MM-YYYY)	Survival Status	If Death, Date of Death (DD-MM-YYYY)	If Death, Cause of Death	Investigator Signature Date (DD-MM-YYYY)
xxxxxx	xxxxxx	DD-MM-YYYY	xxxx	DD-MM-YYYY	xxxxxx	xxxxxx
xxxxxx	xxxxxx	DD-MM-YYYY	xxxx	DD-MM-YYYY	xxxxxx	xxxxxx
xxxxxx	xxxxxx	DD-MM-YYYY	xxxx	DD-MM-YYYY	xxxxxx	xxxxxx
xxxxxx	xxxxxx	DD-MM-YYYY	xxxx	DD-MM-YYYY	xxxxxx	xxxxxx
xxxxxx	xxxxxx	DD-MM-YYYY	xxxx	DD-MM-YYYY	xxxxxx	xxxxxx
xxxxxx	xxxxxx	DD-MM-YYYY	xxxx	DD-MM-YYYY	xxxxxx	xxxxxx
xxxxxx	xxxxxx	DD-MM-YYYY	xxxx	DD-MM-YYYY	xxxxxx	xxxxxx
xxxxxx	xxxxxx	DD-MM-YYYY	xxxx	DD-MM-YYYY	xxxxxx	xxxxxx

Code: S:\Services\Immodulon\IMM-101-008\Analysis\Development\Code\Listing17.sas ddmmmyy:hh:mm:ss

Data: S:\Services\Immodulon\IMM-101-008\xxxxxx.sas7bdat

Note to programmer: Please update data footnote with appropriate file directory.**Note to programmer:** Data is recorded on Post-study Survival Status CRF, with multiple rows per patient (depending on number of occasions long term survival status is assessed).

CONFIDENTIAL**Exploristics Limited**

Identifier: EXP12002

Clinical Study Identifier: IMM-101-008

Final Analysis

Protocol: IMM-101-008

Analysis Population: Safety Population

Page x of y

Listing 18
Additional Comments Recorded

Unique Patient ID	Related Domain	Visit at which comment recorded	Date of Visit (DD-MM-YYYY)	Associated Variable	Comment
xxxxxx	xxxx	xxxxxx	DD-MM-YYYY	xxxx	xxxxxx
xxxxxx	xxxx	xxxxxx	DD-MM-YYYY	xxxx	xxxxxx
xxxxxx	xxxx	xxxxxx	DD-MM-YYYY	xxxx	xxxxxx
xxxxxx	xxxx	xxxxxx	DD-MM-YYYY	xxxx	xxxxxx
xxxxxx	xxxx	xxxxxx	DD-MM-YYYY	xxxx	xxxxxx
xxxxxx	xxxx	xxxxxx	DD-MM-YYYY	xxxx	xxxxxx
xxxxxx	xxxx	xxxxxx	DD-MM-YYYY	xxxx	xxxxxx
xxxxxx	xxxx	xxxxxx	DD-MM-YYYY	xxxx	xxxxxx

Code: S:\Services\Immodulon\IMM-101-008\Analysis\Development\Code\Listing18.sas ddmmmyy:hh:mm:ss

Data: S:\Services\Immodulon\IMM-101-008\xxxxxx.sas7bdat

Note to programmer: Please update data footnote with appropriate file directory.**Note to programmer:** Data is recorded as free text comments on the CRF.**Note to programmer:** Please sort the listing by patient ID and related domain.**Note to programmer:** For any comment relating to AEs, please put the 'AE xx:' in front of the comment.

[figure not shown]
Final Analysis

Protocol: IMM-101-008

Analysis Population: Safety Population

Page x of y

Figure 1a
Panel Plot of On-Study IMM-101 Doses by Patient

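### For any patient who consented to post-withdrawal follow-up after the withdrawal date, SAP 10 counts the gap as time at risk and can bias overall survival upward

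*SAP*

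**What the plan says.** Four parts of the plan bear on this point.

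- **Consent and timing.** Post-withdrawal status was not collected under the initial protocol ("Final Version 1.0, dated 15 th September 2011"). Protocol Appendix 4 records Amendment 4.0, "dated 1 st November 2013 addressed the following changes to the study Protocol", as: "Inclusion of collection of information on subject status following withdrawal from the study subject to provision of informed consent". Protocol 5.2 now reads: "In the case of withdrawal, separate consent will be sought to allow the continued collection on patient status". It sets no time limit for that consent.
- **Censoring.** SAP 10 keeps consenting withdrawn patients in the analysis to death or the date last known alive: "Patients still alive will be censored at withdrawal from the study or at last known date alive if later (where patients have consented". The bracket, cut short here, means agreement to survival follow-up once off study. For the others: "Patients withdrawing from the study without consent for further follow up will be censored for survival at the date of their withdrawal". The post-study data apply to any withdrawn patient and are not limited to withdrawals after Amendment 4.0.
- **Estimator.** SAP 8.3 defines OS as one duration from Day 0 to death or censoring, and SAP 7 applies ordinary Kaplan-Meier. Neither has a late-entry term.
- **Data held.** Listing 17 in SAP 13.2 has a column headed "Date of Consent For Data Collection". The withdrawal date is on CRF page 18.

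**The concern.** Whether a withdrawn patient's later outcome counts depends on something only a living patient can do. If consent comes after withdrawal, surviving the gap is a condition for being counted in it. Survivors of the gap stay in the denominator, while deaths in it never reach the numerator. This is immortal time. It arises even if withdrawal has nothing to do with prognosis and every survivor agrees to follow-up.

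Amendment 4.0 is what makes a gap plausible. Someone who withdrew before it could be brought back only by consenting later.

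OS is the only efficacy endpoint that is summarised (Table 8, Figure 2), because SAP 4 puts metastatic change in listings only. With a single arm, the curve is read on its own and no comparison can cancel an upward shift.

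**Working it through.** The plan gives no expected OS, event count or number of withdrawals, so it has no figure to reproduce. The check covers the date arithmetic, the mechanism, and the size under stated assumptions.

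**1. Dates.** From 15 September 2011 to 15 September 2013 is 731 days, and to 1 November 2013 another 47. That gives 778 / 365.25 = 2.13 years. No Day 0 date is given and Day 0 cannot precede version 1.0, so 2.13 years is the longest a patient could have been on study before the provision existed.

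**2. Mechanism.** Suppose two patients both withdraw at 1.0 year, before the provision. The first is alive at 2.1 years, consents, and is at risk without a break from Day 0 to last known alive. The second dies at 1.5 years and is censored at 1.0. Between 1.0 and 2.1 years the first adds to the risk set and the second's death is not an event.

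**3. Size.** Assumptions, none from the documents: exponential survival with 5-year OS *S* of 30%, 50% or 70%; a fraction *w* of 2/12 or 4/12 withdrawing uniformly over years 0 to 2, independently of prognosis; consent at year 2; all survivors consent. With λ = −ln(*S*)/5 and *t* up to 2 years:

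- alive and not yet withdrawn: a(t) = exp(−λt)(1 − wt/2)
- withdrawn before t and later consenting: b(t) = exp(−2λ) wt/2
- hazard under the SAP rule: λa/(a + b), where the true hazard is λ
- accumulated shortfall: Δ = ∫₀² λb/(a + b) dt
- 5-year OS under the SAP rule: S·exp(Δ), since the hazard is correct after year 2

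Example, S = 0.5 and w = 4/12: λ = 0.1386. At t = 1, a = 0.725 and b = 0.126, so the hazard is 0.1386 × 0.725 / 0.852 = 0.118. Over two years Δ = 0.0428, and 0.5 × exp(0.0428) = 0.522.

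| True 5-year OS | w | Δ | SAP rule | Overstatement (points) |
|---|---|---|---|---|
| 30% | 2/12 | 0.0348 | 31.1% | 1.1 |
| 30% | 4/12 | 0.0705 | 32.2% | 2.2 |
| 50% | 2/12 | 0.0213 | 51.1% | 1.1 |
| 50% | 4/12 | 0.0428 | 52.2% | 2.2 |
| 70% | 2/12 | 0.0114 | 70.8% | 0.8 |
| 70% | 4/12 | 0.0229 | 71.6% | 1.6 |

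Table 8 reports survival quartiles, not 5-year OS. A quartile that falls after year 2 is late by Δ/λ. At S = 0.5 the median of 5.0 years is overstated by 0.0213/0.1386 = 0.15 year or 0.0428/0.1386 = 0.31 year.

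**4. Other withdrawal patterns.** A simulation of 200,000 patients per scenario used constant withdrawal rates and consent from 2.1 years. With true 5-year OS 50%, 10% withdrawing per year and all survivors consenting, the SAP rule gave 77.6%, 59.0% and 44.7% at 2, 4 and 6 years, against true values of 75.7%, 57.4% and 43.5%. Over 5% to 25% per year, 5-year OS of 30% to 70%, and half or all survivors consenting, the overstatement was 0.3 to 5.6 points. Taking the gap out of the risk set came within 0.2 points of truth throughout. With no gap, the bias was zero.

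**5. Withdrawal related to prognosis.** With the death rate tripled after withdrawal (5-year OS 50% on study, 10% per year withdrawing, consent from 2.1 years), 4-year survival was:

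| Method | 4-year survival |
|---|---|
| Truth | 49.6% |
| Re-entry at consent | 52.1% |
| SAP rule | 53.1% |
| Censoring everyone at withdrawal | 57.6% |

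**The case against.** The strongest reply is that the problem may not exist here. Protocol 5.2 ties the request for consent to the withdrawal itself. If consent is signed that day, the gap is nil. Amendment 4.0 says nothing about going back to patients who had already left, and any who were not approached are simply censored at withdrawal, with no immortal time. Protocol 4.2 adds that the patients still on treatment wished to continue, which points to few early withdrawals. All of this stands, so the point has to be conditional.

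Precision also limits it. Protocol 4.2 leaves about 18 − 6 = 12 patients on treatment. One patient is then 1/12 = 8.3 points, and a rough 95% interval around 50% is ±1.96 × √(0.25/12), or ±28 points. A shift of 1 to 2 points is well inside that. The SAP disclaims inference, and Protocol 3.4 says the study is not designed to give evidence of efficacy. A careful reader could also find any gap from Listings 1 and 17. These arguments limit the importance of the point. They do not justify counting time at risk in which a death could not be an event.

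A reader might also take the form described as "Post-Study Long Term Survival Status CRF version 1.0, dated 28 September 2015" to mean that deaths were unrecordable for about four years. The documents do not support that. The date is a form version, not the first date of consent, which Amendment 4.0 allowed from November 2013. Listing 17 holds consent, assessment and death dates separately, so earlier consents and deaths could be entered on a later form.

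**Conclusion.** The mechanism and its direction follow from the SAP's own rules. Wherever consent came after withdrawal, the gap is wrongly kept at risk and OS is biased upward. Whether that happened in this study cannot be settled from the documents, which give no withdrawal counts, consent dates or Day 0 dates. It would be going too far to conclude that the reported curve is too high; the supported statement is that it can be.

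With withdrawal unrelated to prognosis, 2 or 4 of 12 patients leaving in the first two years and consent at year 2, the overstatement of 5-year OS is about 1 to 2 points. It is larger only under heavier assumed withdrawal, and zero if every consent was signed at withdrawal. An individual consent could have come later than November 2013, but no document dates one. This is a modest, conditional point, worth acting on because the check uses dates already held.

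**What to change.** In SAP 8.3 and 10, compare each withdrawn patient's Listing 17 consent date with the CRF page 18 withdrawal date.

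- **Consent on or before withdrawal:** no change.
- **Consent after withdrawal:** close the first interval at withdrawal as censored, and re-enter the patient at the consent date (start/stop Kaplan-Meier). Count follow-up and death only from then. Use this for Table 8 and Figure 2, counting each patient once in the death and censoring totals.
- **Sensitivity analysis:** show the current SAP 10 rule alongside. Censoring everyone at withdrawal is not a safe replacement, because it did worst at 4 years in the prognosis-related example.
- **Table 8 footnote:** give the number of patients whose consent followed withdrawal and each gap in days. If there are none, say so; the analysis then stays as it is.

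The cost is a few lines of SAP text and a start/stop version of the OS dataset, with quartile limits taken from that estimate. Slightly fewer patient-years are at risk, so intervals widen a little and the curve may look less favourable. Re-entry does not recover deaths missed in the gap, and corrects the bias only in part if withdrawal is related to prognosis.
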